Immunogenicity of PPSV-23 after PCV-13 Vaccination in Adult Asthmatic Patients

NCT03260790

6/7/2018

IRB Minimal Risk Protocol Template

Note: If this study establishes a human specimen repository (biobank) for research purposes, do not use this template. Use the Mayo Clinic Human Specimen Repository Protocol Template found on the IRB home page under Forms and Procedures at <http://intranet.mayo.edu/charlie/irb/>

First-time Use: Use this template to describe your study for a new IRB submission.

1. Complete the questions that apply to your study.
2. Save an electronic copy of this protocol for future revisions.
3. When completing your IRBe application, you will be asked to upload this document to the protocol section.

Modification: To modify this document after your study has been approved:

1. Open your study in IRBe. Click on the study 'Documents' tab and select the most recent version of the protocol. Save it to your files.
2. Open the saved document and activate "Track Changes".
3. Revise the protocol template to reflect the modification points , save the template to your files
4. Create an IRBe Modification for the study and upload the revised protocol template.

General Study Information

Principal Investigator: [name]

Study Title: **Immunogenicity of PPSV-23 after PCV-13 Vaccination in Adult Asthmatic Patients**

Protocol version number and date: Protocol version number 3. 06/07/2018

Research Question and Aims

Hypothesis:

- 1) Priming with PCV13 will result in increased immunogenicity of PPSV23 in asthmatic subjects
- 2) Priming with PCV13 will result in durable immunogenicity of the PPSV23 in asthmatic subjects

Aims, purpose, or objectives:

Aim 1 will compare the safety and immunogenicity of PPSV23 and PCV13 vaccines in asthmatic subjects. The vaccine response of randomized asthmatic patients to either PPSV 23 alone (Group A) or PCV13 with PPSV23 given 8 weeks later (Group B) will be compared. Immunogenic response will be assessed and compared between groups at 8 and 16 weeks after vaccination.

Aim 2 will compare the changing of immunologic response in the two arms over the subsequent 8 weeks' time frame in both Group A and Group B.

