**Background (Include relevant experience, gaps in current knowledge, preliminary data, etc.):**

S pneumoniae is the leading bacterial cause of pneumonia and invasive pneumococcal disease and is a significant cause of morbidity and mortality in the United States with \$16.2 billion dollars spent in healthcare-related costs in 2013¹. The CDC currently recommends the polysaccharide PPSV23 vaccination (Pneumovax®) in all adults over the age of 65 as well as in individuals with chronic lung disease.

Pneumococcal conjugate vaccine PCV13 (Prevnar ®), initially developed for use in children, is currently recommended for immunocompromised adults and individuals with cerebrospinal fluid leaks and cochlear implants. There is some debate as to whether PPSV23 leads to a decrease in prevalence of disease caused by *S. pneumoniae*, indeed, a 2009 meta-analysis funded by the WHO found that the evidence supporting its use was poor.² In 2014, vaccination guidelines changed to support the use of PCV13 in patients over the age of 65 after it was found to be efficacious in preventing community acquired pneumonia and invasive pneumococcal disease in the elderly population.³ The PCV13 vaccine contains polysaccharide antigens conjugated with a protein carrier whereas the PPSV23 contains polysaccharide antigens alone. It is proposed that the conjugate vaccine induces immunity via a T-cell dependent process. Given that patients with asthma are disproportionately affected by pneumococcal disease, it is imperative that the vaccination strategy for pneumonia be as immunogenic and efficacious at eliciting a robust immune response as possible.

To address this, we propose to compare the response to PPSV23 with a novel schedule of PCV13 followed by PPSV23 given eight weeks later in adult patients with asthma. We will assess the immune system at 8 weeks and 16 weeks post vaccination. Given that the PCV13 vaccine elicits immunity via a T-cell dependent mechanism, we hypothesize that giving PCV13 in conjunction with PPSV23 will lead to an enhanced immune response in asthmatic patients.

References

1. American Lung Association. Trends in Pneumonia and Influenza Morbidity and Mortality. November 2015.

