Subject ID, subject code or any other person-specific unique identifying number, characteristic or code that can link the subject to their medical data	x	x
Dates: All elements of dates [month, day, and year] directly related to an individual, their birth date, date of death, date of diagnosis, etc.	x	
Note: Recording a year only is not a unique identifier.		
Social Security number		
Medical device identifiers and serial numbers		
Biometric identifiers, including finger and voice prints, full face photographic images and any comparable images		
Web Universal Resource Locators (URLs), Internet Protocol (IP) address numbers, email address		
Street address, city, county, precinct, zip code, and their equivalent geocodes		
Phone or fax numbers		
Account, member, certificate or professional license numbers, health beneficiary numbers		
Vehicle identifiers and serial numbers, including license plate numbers		
Check 'None' when none of the identifiers listed above will be recorded, maintained, or shared during the conduct of this study. (exempt category 4)	 None	 None

Data Analysis

Power analyses and study endpoints are not required for minimal risk research, pilot or feasibility studies.

No statistical information. *If checked, please explain:*

Data Analysis:

For each of the 23 serotypes, exact, unconditional, 2-sided 95% confidence intervals (CIs) on the single proportions will be calculated using the F distribution. The 95% CIs for the difference in proportions ([PCV-13+PPSV23] – [PPSV23]) will be computed using the non-inferiority procedure of Chan and Zhang, using the standardized test statistic and $\gamma=0.000001$. Non-inferiority is declared if the lower CI for the difference is >-0.10 . Similar procedures will be used for the evaluation of antibody concentrations after 12 months.

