For the secondary endpoints, the pneumococcal IgG serotype antibody concentrations will be logarithmically transformed for analysis. Within each treatment group and for each antibody concentration separately, geometric means of the antibody concentrations will be calculated for each vaccine group. Two (2)-sided 95% CIs will be constructed by back transformation of the CIs for the mean of the logarithmically transformed assay results will be computed using the Student *t* distribution. To assess differences between the 2 vaccine groups, the 95% CIs for geometric mean ratio will be computed using the Student *t* distribution for the mean difference of the measures on the log scale ([PCV-13+PPSV23] – [PPSV23]) Non-inferiority will be declared if the lower limit of the CI for the ratio was greater than 0.5 (2-fold criterion). In addition, the geometric mean fold rises from baseline to 12 month following PPSV23 in each arm, and corresponding 2-sided 95% CIs, will be calculated for each of the serotype-specific pneumococcal IgG responses. For formulation decision analyses, 99.8% CIs will be calculated.

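### The hypothesis is that priming increases the response, but the only decision rules test non-inferiority, so meeting them does not support the hypothesis

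*Combined protocol and SAP*

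**What the plan says.** **Hypotheses.** Under Research Question and Aims, Hypothesis 1 is "Priming with PCV13 will result in increased immunogenicity of PPSV23 in asthmatic subjects". The Background repeats the direction: "we hypothesize that giving PCV13 in conjunction with PPSV23 will lead to an enhanced immune response in asthmatic patients". Hypothesis 2 concerns durability and is not at issue here.

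**Decision rules.** Data Analysis contains two. For the difference in proportions, PCV13 plus PPSV23 minus PPSV23: "Non-inferiority is declared if the lower CI for the difference is >-0.10". For the antibody concentrations, introduced as secondary endpoints: "Non-inferiority will be declared if the lower limit of the CI for the ratio was greater than 0.5 (2-fold criterion". The ratio interval has a stated purpose: "To assess differences between the 2 vaccine groups, the 95% CIs for geometric mean ratio will be computed". No rule compares a lower limit with 0 or 1. The event behind the proportions is not defined.

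**Timing.** Aim 1 says: "Immunogenic response will be assessed and compared between groups at 8 and 16 weeks after vaccination". Under Methods, Group A has PPSV23 at week 0 and draws at weeks 0, 8, 16 and 24. Group B has PCV13 at week 0, PPSV23 at week 8, and draws at the same four weeks.

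**Serotypes.** The proportion analysis is run for each of 23 serotypes, and the concentrations are also analysed serotype by serotype. Data Analysis adds 99.8% intervals for a formulation decision that the protocol does not otherwise describe.

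**The concern.** A hypothesis that the response increases calls for a criterion that separates an increase from no increase. A non-inferiority rule only excludes a deficit larger than the margin. If a rule is met, the supported statement is that the primed arm is not worse by more than 10 percentage points, or not below half the comparator's geometric mean. Neither supports Hypothesis 1.

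With no criterion for an increase fixed in advance, any claim of one would have to be framed after the results are known, across 23 serotypes and more than one draw. The trial could then report either a non-inferiority result that does not answer its question or an increase with no prespecified basis.

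**Working it through.** **1. Hypothesis against rule.** The documents give no sample-size derivation, power, SD or responder rate, so there is no planned figure to reproduce, and the main point is logical. Take a GMR interval of 0.55 to 0.95. Its lower limit exceeds 0.5, so non-inferiority is declared. Its upper limit is below 1, so the interval shows a lower response in the primed arm. The rule is met while Hypothesis 1 is contradicted.

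**2. GMR rule, illustration.** Inputs: 50 participants (target accrual) and two-sided 95% Student t intervals on the log scale (Data Analysis). Assumed, because the documents give neither: 25 per arm, and log10 SD 0.5 with range 0.3 to 0.7.

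- SE = SD × √(2/25). At SD 0.5, SE = 0.1414.
- Half-width = t(0.975, 48 df) × SE = 2.011 × 0.1414 = 0.284, a factor of 10^0.284 = 1.92.
- Observed GMR needed for a lower limit above 0.5: 0.5 × 1.92 = 0.96. For a lower limit above 1: 1.92.
- Probability of meeting a threshold c at true ratio g: P(T > 2.011), with T noncentral t on 48 df and noncentrality (log10 g − log10 c)/SE. For g = 1 and c = 0.5 this is 0.301/0.1414 = 2.13, giving 55%.

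| log10 SD | Observed GMR needed, limit > 0.5 | Observed GMR needed, limit > 1 | P(limit > 0.5), true GMR 1.0 | P(limit > 0.5), true GMR 0.75 | P(limit > 1), true GMR 1.0 |
|---|---|---|---|---|---|
| 0.3 | 0.74 | 1.48 | 94% | 53% | 2.5% |
| 0.5 | 0.96 | 1.92 | 55% | 23% | 2.5% |
| 0.7 | 1.25 | 2.50 | 32% | 14% | 2.5% |

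At true ratios of 1.0 and 0.75, non-inferiority at 0.5 is true. The fourth and fifth columns are therefore power, not error rates.

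The example in step 1 is about logic, not likelihood. An interval lying wholly between 0.5 and 1 needs a half-width below log10(2)/2 = 0.1505, so SD below 0.1505/(2.011 × 0.2828) = 0.265 at 25 per arm. At the assumed SDs the usual problem is an interval that clears 0.5 but includes 1.

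**3. Proportion rule.** Exact unconditional test with the standardized score statistic, one-sided 0.025, 25 per arm assumed. With 15/25 responders in Group A, the −0.10 rule is met from 20/25 in Group B, but a lower limit above 0 needs 22/25. So 20/25 and 21/25 pass without showing an increase. With equal true rates between 0.5 and 0.95, the rule is met about 10% to 25% of the time. At this size no tied result passes (25/25 against 25/25 gives p = 0.9^25 = 0.072), so here the mismatch means that an increase is not shown, rather than that an observed deficit is accepted.

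**4. Time.** Counted from PPSV23, Aim 1's 8 and 16 weeks fall on planned draws: weeks 8 and 16 in Group A, and weeks 8 + 8 = 16 and 8 + 16 = 24 in Group B. Counted from week 0, Group B's week-8 draw is at its PPSV23 visit and cannot show a response to that vaccine. Data Analysis does not state the anchor for the rules or which of the two times is the main one.

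**5. Serotypes.** If an increase in any one of 23 unadjusted intervals counted, the chance of at least one false increase would be 1 − 0.975^23 = 44%, assuming independence. A Bonferroni level for 23 is 1 − 0.05/23 = 99.78%, close to the 99.8% in the plan, but that level carries no threshold and no link to Hypothesis 1.

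**The case against.** **The planned intervals already allow an increase to be read off.** This is right, and no data are lost. The ratio interval is explicitly meant for assessing differences. What is missing is a statement of what will count, when, and for which serotypes.

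**The template says power analyses and endpoints are not required for minimal-risk research.** That explains the missing sample-size derivation, and this point does not ask for one. The plan nevertheless states decision rules, and they should match its hypothesis.

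**Stronger readings that the documents do not support.**

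- A reader might infer that the investigators will report non-inferiority as an increase. Nothing in the text says so.
- A reader might take the 55% as a false-positive rate. It is power for a true statement.
- A reader might conclude that no valid comparison time exists. Aim 1 supplies two that fit the draws when counted from PPSV23, and Data Analysis itself counts from PPSV23 in "the geometric mean fold rises from baseline to 12 month following PPSV23 in each arm". The 12-month wording there, and in "Similar procedures will be used for the evaluation of antibody concentrations after 12 months", has no matching draw, but that is a separate defect.
- A reader might say that serotypes outside the conjugate vaccine cannot be primed. A 13-valent vaccine leaves at least 23 − 13 = 10 of the 23 unshared, but the documents do not list the serotypes or say that priming is impossible for them.

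**Conclusion.** The point holds, and the plan needs correcting. Hypothesis 1 and the Background predict an increase; both written rules are non-inferiority, and meeting either does not support an increase. This rests on the text alone and on no assumed figure.

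The illustrative size, 55% against 2.5% per serotype at a true ratio of 1, depends on the assumed 25 per arm and log10 SD. The 55% ranges from 94% to 32% over SD 0.3 to 0.7; the 2.5% does not change. The unstated main time and the missing rule for 23 serotypes are smaller, linked gaps, to be closed in the same edit.

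**What to change.** Keep the sample size, the draws and the planned 95% intervals. Amend the wording of Data Analysis as follows.

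1. **Criterion.** Hypothesis 1 is supported only if the lower limit of the planned interval exceeds 1 for the GMR, or 0 for the difference in proportions once the responder event is defined. Keep −0.10 and 0.5 as non-inferiority statements that are not evidence of an increase. Reading one interval at both thresholds costs no alpha. Alternatively, restate Hypothesis 1 as non-inferiority and claim no increase.
2. **Endpoint hierarchy.** The plan lists the GMR under secondary endpoints. If it becomes the criterion for Hypothesis 1, say so openly.
3. **Time.** Apply the criterion at Aim 1's times counted from PPSV23 (weeks 8 and 16 in Group A, weeks 16 and 24 in Group B) and name one as the main time.
4. **Serotypes.** State how the per-serotype results bear on Hypothesis 1, for example with a multiplicity-adjusted level reconciled with the 99.8% intervals already in the plan, or label them descriptive. Reporting the serotypes shared with the 13-valent vaccine separately is optional.

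**Cost.** Protocol wording and a few decisions, made before any comparison of titers between arms; no new data. The downside to state is modest power for an increase. With 25 per arm and an unadjusted 95% interval, power per serotype is 23% at a true GMR of 1.5 and 55% at 2.0 (SD 0.5); 53% and 94% (SD 0.3); 14% and 32% (SD 0.7). Any multiplicity adjustment lowers these figures.

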
Study Design and Methods**Methods: Describe, in detail, the research activities that will be conducted under this protocol:**

Subjects: 50 adult patients diagnosed with asthma will be recruited from patients seen in the Division of Allergic Diseases and from Primary Care; volunteers will also be solicited with flyers and electronic announcements. The patients recruited will be between 19 and 64 years of age. Exclusion criteria include

research exemption requested, history of PCV-13 vaccination, age \leq 19 or \geq 64, history of cochlear implant, CSF leak, CHF, DM, CKD, HIV, CVID as well as patients who have received the PPSV23 vaccine in the last 5 years. Women who are pregnant will also be excluded from the study. They will be contacted at the end of their visit to discuss enrollment in the study by the research coordinator.

Protocol: The patients will then be randomized into either Group A (standard of care) or Group B (experimental group). At the week 0 time point, the patients will receive either PPSV23 vaccine (Group A) or PCV13 (Group B) and undergo a blood draw of 5mL for assessment of pre-vaccination serotype titers. Group A will undergo a 5mL draw for assessment of titers at week 8, 16, and 24 following vaccination. Group B will undergo vaccination with PPSV23 at Week 8 with 5mL draw for pneumococcal serotype titers as well as a blood draw at Week 16 and Week 24. Immunogenicity will be analyzed by assessing for serotype-specific IgG as well as total IgG binding. Samples will be run at Mayo Rochester, and samples will additionally be shipped to a third party, The Binding Site, for further antipneumococcal binding assays. The samples will be identified to The Binding Site only by their study-specific identification number (i.e. A01, B01 etc). The Binding Site will not receive any patient identifying information.

Resources: *Describe the available resources to conduct the research (personnel, time, facilities, mentor commitment, etc.):*

This study is being conducted by [name], [name], [name], and [name]. [name], PGY4, has 9 months of dedicated research time.

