(1a) This is a multisite study involving Mayo Clinic and non Mayo Clinic sites. *When checked, describe in detail the research procedures or activities that will be conducted by Mayo Clinic study staff.*

(1b) Mayo Clinic study staff will be engaged in research activity at a non Mayo Clinic site. *When checked, provide a detailed description of the activity that will be conducted by Mayo Clinic study staff.*

Subject Information

Target accrual is the proposed total number of subjects to be included in this study at Mayo Clinic. A "Subject" may include medical records, images, or specimens generated at Mayo Clinic and/or received from external sources.

Target accrual: 50

Subject population (children, adults, groups): Adults

Inclusion Criteria: Ages 19 to 64 with diagnosis of asthma

Exclusion Criteria: Exclusion criteria include research exemption requested, history of PCV-13 vaccination, age $<$ 19 or $>$ 65, history of cochlear implant, CSF leak, CHF, DM, CKD, HIV, CVID as well as patients

who have received the PPSV23 vaccine in the last 5 years. Women who are pregnant will also be excluded from the study by performing 2 point of care urine pregnancy tests (prior to vaccinations)

Research Activity

Check all that apply and complete the appropriate sections as instructed.

1. **Drug & Device:** Drugs for which an investigational new drug application is not required. Device for which (i) an investigational device exemption application is not required; or the medical device is cleared/approved for marketing and being used in accordance with its cleared/approved labeling. (Specify in the Methods section)
2. **Blood:** Collection of blood samples by finger stick, heel stick, ear stick, or venipuncture.
3. **Biological specimens other than blood:** Prospective collection of human biological specimens by noninvasive means that may include: urine, sweat, saliva, buccal scraping, oral/anal/vaginal swab, sputum, hair and nail clippings, etc.
4. **Tests & Procedures:** Collection of data through noninvasive tests and procedures routinely employed in clinical practice that may include: MRI, surface EEG, echo, ultrasound, moderate exercise, muscular strength & flexibility testing, biometrics, cognition testing, eye exam, etc. (Specify in the Methods section)
5. **Data** (medical record, images, or specimens): Research involving use of existing and/or prospectively collected data.

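### The geometric mean ratio non-inferiority comparison ignores the week-0 titres collected in both arms; the interval is valid but may be wider than it needs to be

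*Combined protocol and SAP*

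**What the plan says.** The Data Analysis section states for the secondary endpoints that "the pneumococcal IgG serotype antibody concentrations will be logarithmically transformed for analysis". For the between-arm step, "the 95% CIs for geometric mean ratio will be computed using the Student" *t* distribution, applied to the mean log-scale difference (PCV13 then PPSV23, minus PPSV23 alone). No covariate is named there, and no baseline-adjusted arm comparison appears elsewhere in the document. The decision rule is "Non-inferiority will be declared if the lower limit of the CI for the ratio was greater than 0.5 (2-fold criterion").

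The Protocol paragraph of Study Design and Methods has participants in both arms "undergo a blood draw of 5mL for assessment of pre-vaccination serotype titers" at week 0. The only use of these values in the Data Analysis section is a fold-rise summary: "the geometric mean fold rises from baseline to 12 month following PPSV23 in each arm". That summary is made within each arm and leaves the between-arm interval unchanged.

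The Subject Information section gives "Target accrual: 50". The allocation ratio is not stated.

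**The concern.** The non-inferiority verdict for each serotype depends on where the lower confidence limit falls relative to 0.5. In a trial of 50, that depends heavily on the width of the interval. If a participant's week-0 titre predicts the later titre of the same serotype, the unadjusted *t* interval leaves that explainable variation in the error term. A serotype that is truly non-inferior is then more likely to miss the margin than the collected data require.

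Enrolment can also mix pneumococcal vaccination histories, because PPSV23 is an exclusion only if given in the last 5 years. That is a reason to expect spread in week-0 titres, but it does not establish how strongly they predict the response.

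This is a question of efficiency. It does not imply bias or an inflated error rate.

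**Working it through.** **Inputs from the documents.** Total 50 (Subject Information); margin 0.5 on the ratio, which is log10(2) = 0.301 on the log10 scale; two-sided 95% interval (Data Analysis); week-0 titres in both arms (Study Design and Methods). The plan states no power, SD or sample-size calculation, so there is no figure of its own to reproduce.

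**Assumptions not in the documents.** 1:1 allocation, so n = 25 per arm; no dropout (n = 20 per arm as a sensitivity case); log10 SD of 0.5 (0.4 and 0.6 as alternatives), equal in both arms; true ratio 1; correlation r between log week-0 and log post-vaccination titre from 0 to 0.7, equal in both arms.

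**Formulas.**
- Unadjusted: SE = SD × √(2/n), with 2n − 2 df.
- ANCOVA: SE = SD × √(1 − r²) × √(2/n) × √(1 + 1/(2n − 4)), with 2n − 3 df. The last factor is the expected cost of chance baseline imbalance.
- The interval is the estimate multiplied and divided by 10^(t × SE).
- Power is the probability that the lower limit exceeds 0.5, from the noncentral *t* distribution.

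**Unadjusted, n = 25, SD 0.5.** SE = 0.5 × √(2/25) = 0.1414; t(48 df) = 2.011; half-width 0.2843; factor 10^0.2843 = 1.92. The observed ratio must be at least 0.5 × 1.92 = 0.96 to pass. Power is 55%.

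**ANCOVA at r = 0.5.** SE = 0.5 × √0.75 × √(2/25) × √(1 + 1/46) = 0.1238; t(47 df) = 2.012; half-width 0.2491; factor 1.77. The observed ratio must be at least 0.89. Power is 66%.

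| Analysis | Factor | Change in log-scale width | Power |
|---|---|---|---|
| Unadjusted | 1.92 | – | 55% |
| ANCOVA, r = 0 | 1.94 | +1% | 54% |
| ANCOVA, r = 0.2 | 1.91 | −1% | 56% |
| ANCOVA, r = 0.3 | 1.88 | −3.5% | 58% |
| ANCOVA, r = 0.5 | 1.77 | −12% | 66% |
| ANCOVA, r = 0.7 | 1.60 | −28% | 82% |

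The two methods break even at r of about 0.15 (0.17 with 20 per arm).

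**Sensitivity to SD and n** (power at true ratio 1):

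| Case | Unadjusted | r = 0.3 | r = 0.5 | r = 0.7 |
|---|---|---|---|---|
| n = 25, SD 0.4 | 74% | 77% | 84% | 95% |
| n = 25, SD 0.6 | 41% | 44% | 51% | 67% |
| n = 20, SD 0.5 | 46% | 48% | 56% | 73% |

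**Sensitivity to the true ratio** (n = 25, SD 0.5; 1.25 and 1.5 are illustrative):

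| True ratio | Unadjusted | r = 0.3 | r = 0.5 |
|---|---|---|---|
| 1.25 | 78.7% | 81.5% | 88.3% |
| 1.5 | 91.1% | 92.9% | 96.5% |

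**Validity.** In 40,000 simulated trials per correlation with the true ratio at the margin (n = 25, SD 0.5), the one-sided error rate was 2.5% for the unadjusted interval at every r tried, and 2.4% to 2.6% for ANCOVA.

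**Could a between-arm comparison of fold rises serve instead?** With equal SDs, the variance of a change-score comparison relative to the unadjusted one is 2(1 − r): 1.40, 1.00 and 0.60 at r = 0.3, 0.5 and 0.7. For ANCOVA it is 1 − r²: 0.91, 0.75 and 0.51. A change score does worse than ANCOVA at each of these values.

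**The case against.** The planned interval is a valid, pre-specified analysis that contradicts nothing else in the document, so replacing it could be called a matter of taste. The endpoint is secondary, it is read serotype by serotype, no overall success rule hangs on any one ratio, and the template says power analyses are not required for a study of this kind. The gain rests on a correlation the documents do not give. It is nil or slightly negative below about 0.15, small at 0.3, and material only from about 0.5. The two arms follow different vaccine schedules, so the correlation and SD need not be equal across arms. Finally, the protocol's first hypothesis expects more immunogenicity after priming, so a true ratio of 1 shows adjustment in a favourable light: at a ratio of 1.5 and r = 0.5 the gain is about 5 points, against 11 at a ratio of 1.

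Most of this stands as a limit on size. No error is present, the benefit is uncertain and will differ across serotypes, and a ratio above 1 reduces the power gain. None of it reverses the direction once r exceeds about 0.15, and the narrowing of the interval does not depend on the true ratio. The possible loss is about 1% in width, while the possible gain is several times larger. The choice has to be made before results are seen, since adding a covariate afterwards invites selection.

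**Conclusion.** The point holds as a loss of precision on a secondary endpoint. The between-arm ratio is compared without adjustment although a suitable covariate is measured in both arms before vaccination. With 25 per arm, ANCOVA would narrow the log-scale interval by 3.5%, 12% and 28% at correlations of 0.3, 0.5 and 0.7, and widen it by about 1% at zero. These percentages do not depend on the SD or the true ratio. The power figures do: the move from 55% to 66% at r = 0.5 assumes a log10 SD of 0.5, a true ratio of 1, 1:1 allocation and no dropout. The documents do not show where the correlation lies, so the gain is possible but not assured. The change is worth making because it costs almost nothing.

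**What to change.** In the secondary-endpoint paragraph of the Data Analysis section, replace the unadjusted between-arm interval as follows.

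- For each serotype, fit an ANCOVA to log concentration with terms for arm and log week-0 concentration of the same serotype. Back-transform the arm effect and its 95% interval, and keep the 0.5 margin.
- Define baseline as week 0 in both arms. The plan says "Group B will undergo vaccination with PPSV23 at Week 8 with 5mL draw", so Group B's week-8 sample comes after PCV13 and is not a pre-treatment value. The fold-rise wording does not settle which draw serves as baseline.
- Name the draw to which the model applies. The scheduled draws end at week 24, whereas the Data Analysis section refers to 12 months. These passages must be reconciled before the model's outcome is defined.
- Keep the unadjusted *t* interval as a sensitivity analysis.

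Once the time point is fixed, this is a short edit. It needs no new visit, sample or assay. It uses one degree of freedom and, if baseline carries no information, widens the interval by about 1% with 25 per arm.

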6. **Digital Record:** Collection of electronic data from voice, video, digital, or image recording. (Specify in the Methods section)
7. **Survey, Interview, Focus Group:** Research on individual or group characteristics or behavior, survey, interview, oral history, focus group, program evaluation, etc. (Specify in the Methods section)

NIH has issued a *Certificate of Confidentiality* (COC). *When checked, provide the institution and investigator named on the COC and explain why one was requested.* _____

Biospecimens – Categories 2 and 3

(2) Collection of blood samples. When multiple groups are involved copy and paste the appropriate section below for example repeat section b when drawing blood from children and adults with cancer.

a. **From healthy, non-pregnant, adult subjects who weigh at least 110 pounds.** For a minimal risk application, the amount of blood drawn from these subjects may not exceed 550ml in an 8 week period and collection may not occur more frequently than 2 times per week.

Volume per blood draw: 15 ml

Frequency of blood draw (e.g. single draw, time(s) per week, per year, etc.) 4 times per year _____

b. **From other adults and children considering age, weight, and health of subject.** For a minimal risk application, the amount of blood drawn from these subjects may not exceed the lesser of 50 ml or 3 ml per kg in an 8 week period, and collection may not occur more frequently than 2 times per week.

Volume per blood draw: 15 ml

Frequency of blood draw (e.g. single draw, time(s) per week, per year, etc.) _____

(3) Prospective collection of biological specimens other than blood: _____

Review of medical records, images, specimens – Category 5

For review of existing data: provide a date range or an end date for when the data was generated. The end date can be the date this application was submitted to the IRB. Example: *01/01/1999 to 12/31/2015* or all records through *mm/dd/yyyy*.

Date Range:

Check all that apply (data includes medical records, images, specimens).

(5a) Only data that exists before the IRB submission date will be collected.

(5b) The study involves data that exist at the time of IRB submission **and** data that will be generated after IRB submission. Include this activity in the Methods section.

Examples

- The study plans to conduct a retrospective chart review and ask subjects to complete a questionnaire.

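### Two planned analyses are set at 12 months, but the last scheduled blood draw is at week 24

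*Combined protocol and SAP*

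**What the plan says.** Two sentences in Data Analysis name 12 months. The first closes the paragraph on proportions and non-inferiority: "Similar procedures will be used for the evaluation of antibody concentrations after 12 months". It gives no time origin. The second is in the paragraph on secondary endpoints and counts from the polysaccharide vaccine: "the geometric mean fold rises from baseline to 12 month following PPSV23 in each arm", with a 95% CI for each serotype.

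Sampling is set out under Study Design and Methods. At week 0 Group A receives PPSV23 and Group B receives PCV13, and all subjects "undergo a blood draw of 5mL for assessment of pre-vaccination serotype titers". After that, "Group A will undergo a 5mL draw for assessment of titers at week 8, 16, and 24 following vaccination". Group B receives "PPSV23 at Week 8 with 5mL draw for pneumococcal serotype titers as well as a blood draw at Week 16 and Week 24". No later sample is scheduled anywhere in the document.

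Research Question and Aims sets shorter times. Hypothesis 2 reads "Priming with PCV13 will result in durable immunogenicity of the PPSV23 in asthmatic subjects". For Aim 1, "Immunogenic response will be assessed and compared between groups at 8 and 16 weeks after vaccination". Aim 2 compares how the response changes in the two arms over a further 8 weeks.

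**The concern.** The analysis section asks for antibody measurements at a time when no blood is taken. Durability is one of the two hypotheses, and Data Analysis names no follow-up time other than 12 months. Once that time proves impossible, the section names no collected visit for any of its analyses. The visit that is reported could then be chosen after the data are seen. A reader of the plan could also expect a one-year durability result from a study that follows subjects for less than half a year after PPSV23.

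**Working it through.** The plan states no sample-size or power figure that bears on this point, so there is none to reproduce. The check is schedule arithmetic.

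**Inputs** (Study Design and Methods; Data Analysis)
- Draws in both arms: study weeks 0, 8, 16, 24.
- PPSV23: week 0 in Group A, week 8 in Group B.
- Time required: 12 months, taken as 52 weeks.

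**Step 1. Weeks since PPSV23 at each draw** = draw week − PPSV23 week

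| Study week of draw | Group A | Group B |
|---|---|---|
| 0 | 0 | −8 |
| 8 | 8 | 0 |
| 16 | 16 | 8 |
| 24 | 24 | 16 |

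**Step 2. Shortfall for the fold rise, counted from PPSV23**
- Group A: needed at week 0 + 52 = 52; last draw 24; shortfall 52 − 24 = 28 weeks.
- Group B: needed at week 8 + 52 = 60; last draw 24; shortfall 60 − 24 = 36 weeks.

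**Step 3. Shortfall for the other 12-month sentence, which has no stated origin**
- From first vaccination: 52 − 24 = 28 weeks in both arms.
- From PPSV23: 28 weeks (A) and 36 weeks (B), as in step 2.

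Under either origin, none of the four scheduled draws falls at 12 months.

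**Step 4. What the schedule does support**
- The post-PPSV23 times sampled in both arms are 8 weeks (A: week 8; B: week 16) and 16 weeks (A: week 16; B: week 24). The later of these, 16 weeks, is the limit for a comparison aligned on PPSV23.
- Aim 1's 8 and 16 weeks are sampled in both arms whether counted from first vaccination (weeks 8 and 16) or from PPSV23.

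**Step 5. Baseline for the fold rise**
- In Group A, week 0 precedes the only vaccine given, so there is one candidate.
- In Group B there are two. Week 0 precedes PCV13, so a rise from week 0 to week 24 reflects the whole sequence. Week 8 is the PPSV23 visit. If that draw is taken before the injection, which the text does not state, a rise from week 8 to week 24 isolates the change after PPSV23.
- The plan says only baseline, and the two choices estimate different things.

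**The case against.** The strongest reply is that little of the study depends on month 12. The aims set their own times in weeks, and the scheduled samples serve Aim 1. The between-arm difference in proportions and the geometric mean ratio are written without a time and can be computed at any collected visit. The 12-month wording affects one sentence extending the proportion procedures and one within-arm secondary summary. This stands. A reader might infer that the trial cannot address durability at all, or that its between-arm comparisons fail. The documents do not support either inference.

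The Data Analysis form also notes that minimal-risk studies need not give power analyses or endpoints. That excuses leaving an analysis out. It does not supply data for one that has been written in.

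The blood-collection form gives a frequency, "per year, etc.) 4 times per year", and a reader might take this as proof that no fifth draw exists. It is a rate rather than a total, so it is only loosely consistent with four draws. The finding rests on the visit schedule.

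A reader might also infer that Aim 2 has no method. Its comparison of change is not written out, but the log-scale Student t interval given for the geometric mean ratio extends directly to a difference in log change. What is missing is detail: the window and its origin. Counted from first vaccination, the further 8 weeks run from week 16 to week 24 and are sampled in both arms. Counted as 16 to 24 weeks after PPSV23, Group B would need week 8 + 24 = 32, which is not sampled.

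**Conclusion.** Wrong as written, and to be corrected before analysis. Both 12-month statements call for data that the schedule does not produce. For the fold rise the last draw is 28 weeks (Group A) and 36 weeks (Group B) too early. For the other statement the gap is at least 28 weeks whichever origin is used. The only assumptions are that 12 months means 52 weeks and that the visit schedule in Study Design and Methods is complete. The result does not depend on sample size, margin or variability.

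The documents do not show whether 12 months is a wording slip or whether a late draw was intended and left out. The effect is confined to those two statements and to any one-year durability claim. The unclear Aim 2 window is a minor clarification and would not justify this rating alone.

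**What to change.** Reconcile Research Question and Aims, Study Design and Methods, and Data Analysis so that every analysis names a collected visit. With the scheduled samples:

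1. **Fold rise.** Replace 12 months with 16 weeks after PPSV23 (Group A: week 16; Group B: week 24), the latest time after PPSV23 sampled in both arms.
2. **Other 12-month sentence.** Name the collected visit or visits at which the procedures will be applied.
3. **Baseline in Group B.** State whether it is week 0, so that the rise includes the PCV13 response, or week 8, so that it reflects PPSV23 alone. If week 8, say that the draw precedes the injection. The documents leave this choice open and the sponsor should make it.
4. **Minor clarification.** State whether Aim 1's 8 and 16 weeks, and Aim 2's further 8 weeks, count from first vaccination or from PPSV23. Say that the log-scale t interval will be applied to the between-arm difference in change over the Aim 2 window.

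The cost is wording only, settled before the data are analysed. The downside is scope: the between-arm durability conclusion is limited to 16 weeks after PPSV23. If a 12-month conclusion was intended, it needs a draw that the schedule lacks, at about week 52 in Group A and week 60 in Group B when counted from PPSV23, with follow-up extended to match.
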